#### 3.2.2.3 Blood eosinophils and sputum free eosinophils cationic protein

The change, expressed as a ratio, in blood and sputum free ECP concentrations from baseline up to Week 12 (Visit 9) is a secondary endpoint. The ratio of Week 12 (Visit 9) to baseline will be calculated as described in Section 3.1.2 and compared between treatments. Absolute change from baseline to Week 12 (Visit 9) will be calculated as a supportive variable.

#### **3.2.3 Efficacy Exploratory Variables**

#### 3.2.3.1 Biomarkers for airway inflammation

The change from baseline to Week 12 (Visit 9) will be calculated as described in Section 3.1.2, and separately expressed as absolute change, percent change, for all exploratory endpoints:

- The number of eosinophils per mm^2 of epithelium and airway smooth muscle bundle.
- Inflammatory cell counts/mm^2 of epithelium, submucosa and airway smooth muscle bundle for:
  - CD3+, CD4+, CD8+ lymphocytes
  - Neutrophils
  - Macrophages
  - Mast Cells.
- Induced sputum for:
  - Number and percentage of neutrophils, lymphocytes and macrophage as percentage number of inflammatory cells
- Serum:
  - Biomarkers which may include (but are not limited to) periostin, DPP4.
- Blood total IgE.
- FENO.

#### 3.2.3.2 Effect on large airways remodelling

The change from baseline to Week 12 (Visit 9) will be calculated as described in Section 3.1.2 for the following exploratory endpoints:

- Airway epithelial cell integrity.
- Lamina reticularis and RBM thickening.
- Deposition of periostin in basement membrane.
- Mucus glands and MUC5A.
- Biomarkers of tissue remodelling and/or destruction which may include but are not limited to  $\alpha$ -SMA and collagen type IV, fibronectin, laminin tenascin and TGF $\beta$  and epithelial damage markers which may include caspase 3 and CC16/KL6
- Large airway dimensions and estimated airway resistance determined from CT:
  - Morphology parameters (Lumen area, wall area and wall area %) for airway generations 3, 4 and 5 (segmental, sub-segmental). For these analyses, only the percent change will be considered. In case of several records per subject/ parameter/ visit, the subject/ parameter/ visit average will be calculated first. The percent change from baseline will then be calculated for each subject/ parameter. Analyses will then be done separately for RB1 and LB1+2. The average percent change from baseline will also be calculated across all segmental parameters, and across all sub-segmental parameters; then summarized separately.
  - Airway resistance for airway generations 3, 4 and 5 estimated based on lumen area (airway resistance=(Lumen Area)). For these analyses, only the percent change will be considered. In case of several records per subject/ parameter/ visit, the subject/ parameter/ visit average will be calculated first. The percent change from baseline will then be calculated for each subject/ parameter. Analyses will then be done separately for RB1 and LB1+2. The average percent change from baseline will also be calculated across all segmental parameters, and across all sub-segmental parameters; then summarized separately.

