#### 4. ANALYSIS METHODS

#### 4.1 General principles

The analysis of the study endpoints will include all data captured during the 12-week doubleblind treatment period. This includes data regardless of whether IP was prematurely discontinued or delayed, and/or irrespective of protocol adherence, unless the subject withdraws consent to study participation.
Only exacerbations confirmed to meet the protocol definition (CSP Section 5.1.12) will be included in exploratory summaries. This includes only exacerbations that started on or after the date of randomisation, and those that are defined as a worsening of asthma that leads in at least one of the three criteria detailed in protocol Section 5.1.12 being fulfilled. This will include exacerbations where the eCRF exacerbation records a new/worsened symptom, requiring systemic corticosteroid intervention or hospitalization.

A summary table which counts subjects who have been incorrectly randomized and who received incorrect treatment will be presented.

Summary data will be presented in tabular format by treatment. Categorical data will be summarized by the number and percentage of subjects in each category. Continuous variables for parametric data will be summarized by descriptive statistics including N, mean, standard deviation (SD), geometric mean, SD of log values, median, minimum and maximum. All data will be listed. Data listings will be sorted by treatment and subject number.

Measures of location (mean, geometric mean, median, minimum and maximum) will be reported to the same degree of precision as the raw data unless otherwise stated. Measures of spread (SD) will be reported to one further degree of precision.

Continuous descriptive statistics for the percent and absolute change from baseline will summarize N, mean, SD, median, minimum and maximum and will be based on raw data. Continuous descriptive statistics for the ratio will summarize N, geometric mean and SD of log values and will be based on log-transformed data. Primary and secondary efficacy variables will summarise the ratio, absolute and percent change, exploratory efficacy variables will summarise absolute and percent change, and non-efficacy summary statistics on the change from baseline will only present the absolute change.

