# 6. CHANGES OF ANALYSIS FROM PROTOCOL

A number of clarifications and minor corrections have been made and are listed below:

- Section 3.4.3/4.2.9.2: due to the way the data is collected on the eCRF, the urinalysis categories have been updated to negative, trace or positive.
- The presentation of asthma exacerbations is not detailed in the protocol. This has been added as an exploratory variable (Section 1.1.4) and some text detailing summaries that will be provided have been included In addition, a start and end date definition of an exacerbation has also been added.
- Section 3.3.1.5: Categorisation of Improved/ No Change/ Deterioration has be relabelled as ACQ-6 Response to be distinct from ACQ-6 Responder which is Yes or No.
- Section 1.1.4 p.15: The analysis is now calculate the change from baseline up to Week 12 in fractional exhaled nitric oxide ( $FE_{NO}$ )
- Section 3.1.1: Baseline for Asthma Daily Diary variables will be, for each variable, the average of all the daily records within the 14 days prior to randomization
- Section 3.2.3.1 to Section 3.2.3.3: ratios will also be calculated for sputum, serum, large and small airways remodelling variables
- Section 3.3.1.3: Bi-weekly mean number of nights is expressed as a percentage
- Section 3.4.1 and 4.2.2: increased follow-up period to 20 weeks
- Section 1.1.4 and 3.2.3.2, 3.2.3.3: The three types of change from baseline analyses (absolute, percent, ratio) will be performed for all exploratory endpoints.
- Section 3.2.3.1: Removed analysis of soluble biomarkers, serum biomarker, nasosorption biomarkers, airway epithelial gene expression, airway volume and resistance based on FRI, effect of Tralo on RNA.
- Removed references to sub-sub segmental as team will be combining sub-segmental and sub-sub-segmental analyses together.
- SNOT-20 is coming from RAVE, and not from the e-diary data.
- The change in sputum eosinophils as percentage number of inflammatory cells won't be analysed (this was a supportive secondary outcome measure added in protocol amendment 2).
- MMRM only performed on secondary efficacy; not on efficacy

- Section 2.1.3: The definition of PK analysis set has been updated to include subjects in FAS who received tralokinumab and had blood samples obtained for PK.
- Section 3.4.2: The OAEs have been updated to safety topics of special attention
- Section 4.1: Under general principles, the p-values rounding has been updated from 3 to 4 decimal places (reference CSP section: 8.5).

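### Airway resistance, defined as lumen area to the power -2, is summarised as an arithmetic mean of percent changes, which shifts the within-arm figure upward and can set it against the lumen-area figure from the same scans

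*SAP*

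**What the plan says.** SAP 3.2.3.2 gives the definition "Airway resistance for airway generations 3, 4 and 5 estimated based on lumen area (airway resistance=(Lumen Area) -2", where the -2 is an exponent. For the morphology measures and for resistance alike it states "For these analyses, only the percent change will be considered". The order of operations is:

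- Repeat records within a visit are averaged.
- Each subject then gets one percent change per parameter.
- Two named airways, RB1 and LB1+2, are each analysed on their own.
- In addition, percent changes are pooled over airways: "The average percent change from baseline will also be calculated across all segmental parameters, and across all sub-segmental parameters; then summarized separately".

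SAP 4.1 fixes the statistics. For change scores, "Continuous descriptive statistics for the percent and absolute change from baseline will summarize N, mean, SD, median, minimum and maximum", computed on untransformed data. For ratios, "Continuous descriptive statistics for the ratio will summarize N, geometric mean and SD of log values", computed on logs. The same section gives exploratory efficacy variables absolute and percent change, with no ratio.

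SAP Section 6 says otherwise. Against Sections 3.2.3.1 to 3.2.3.3 it records that "ratios will also be calculated for sputum, serum, large and small airways remodelling variables". A later bullet, which cites 3.2.3.2, promises absolute, percent and ratio analyses for every exploratory endpoint. Neither statement is carried into 3.2.3.2 or 4.1.

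**The concern.** In any one airway, log R = -2 log LA exactly (R resistance, LA lumen area). Resistance adds no information beyond lumen area, so the two summaries should tell one story. Arithmetic means of percent change break that link. A halving and a doubling of lumen area cancel on the log scale but not on the percent scale, and the imbalance is much larger for LA to the power -2 than for LA.

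For the airway-averaged summary, the averaging takes place inside each subject's value before any summary over subjects. The shift is then already in the subject-level number, and the median over subjects cannot fully take it out.

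What is at stake is interpretation. SAP 4.2.6 presents these outcomes descriptively, with no model, so the by-arm figures are what a reader sees. An arm could show lumen area up and resistance up. A true widening could appear as a smaller fall in resistance than occurred, or as no fall. A programmer who follows 3.2.3.2 literally would produce no ratio to put beside it.

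**Working it through.** **Inputs.** R = LA to the power -2, percent change only, and percent change taken before averaging over airways (SAP 3.2.3.2); mean and median on raw data (SAP 4.1). The documents state no variability or expected effect for the CT measures, so there is no plan figure to reproduce. The log SDs of 1.62 and 1.82 in SAP 1.3 belong to the eosinophil endpoint and cannot be used here. I assume the per-airway change d = log(LA at Week 12 / LA at baseline) is normal with mean m and SD s, and show a range of s.

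**Illustration without a distribution.** One airway goes to 1.25 times baseline and another to 0.80 times. The log changes cancel, because 1.25 x 0.80 = 1.
- Lumen area: (25 - 20)/2 = +2.5%.
- Resistance: 1.25^-2 = 0.64 (-36%) and 0.80^-2 = 1.5625 (+56.25%), mean +10.1%.

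**Within-arm mean.** Mean percent change in LA = exp(m + s²/2) - 1. Mean percent change in R = exp(-2m + 2s²) - 1.

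| s | LA, no true change | R, no true change | R reported when every airway truly widens 10% (true R -17.4%) |
|---|---|---|---|
| 0.1 | +0.5% | +2.0% | -15.7% |
| 0.2 | +2.0% | +8.3% | -10.5% |
| 0.3 | +4.6% | +19.7% | -1.1% |

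Example for the last column at s = 0.2: 1.10^-2 x exp(0.08) = 0.8264 x 1.0833 = 0.895, or -10.5%.

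Expected mean R rises whenever m is below s². A true lumen-area gain of up to exp(s²) - 1, that is 1.0%, 4.1% or 9.4% at s = 0.1, 0.2 or 0.3, would thus appear with a rise in mean resistance.

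Averaging over more airways does not reduce the shift. In simulation at s = 0.2 with between-airway correlation 0.3, mean R is +8.2% with one or two airways and +8.3% with six. With 40 subjects, two airways and no true change, both arm means rise in 42%, 71% and 86% of simulated trials at s = 0.1, 0.2 and 0.3.

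**Median.** For a single airway, R is a monotone function of LA, so the median of R follows the median of LA and the shift is essentially absent. For the airway average it remains. With no true change and 10 airways per subject, the median percent change in resistance is:

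| Correlation between airways | s = 0.2 | s = 0.3 |
|---|---|---|
| 0 | +7.1% | +17.0% |
| 0.3 | +5.3% | +11.5% |
| 0.6 | +2.7% | +6.4% |
| 0.8 | +1.4% | +2.9% |

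**Between arms.**
- Equal s = 0.3, true LA +5% on tralokinumab. LA: 1.05 x 1.046 - 1.046 = +5.2 points. R: (1.05^-2 - 1) x 1.197 = -11.1 points. The signs are opposite, as they should be.
- Unequal s (0.3 on tralokinumab, 0.2 on placebo), true LA +3%. LA: 7.7 - 2.0 = +5.7 points. R: 1.03^-2 x exp(0.18) = 1.128, so 12.8 - 8.3 = +4.5 points. Both are positive, which is contradictory. In simulation with two airways and 40 subjects per arm, both differences are positive in 53% of trials.

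**On the log scale.** Mean log R = -2 x mean log LA identically. The shift with no true change is zero, and the two measures cannot disagree in direction.

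**The case against.** The case on the other side is substantial.

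- **The airway average is not the only summary.** A reader might infer that resistance is reported only after averaging over airways. SAP 3.2.3.2 also analyses RB1 and LB1+2 separately, and SAP 4.1 reports the median. There the median is unbiased, and no subject can show both measures rising. This stands. The mean remains shifted in those summaries too.
- **The size depends on unknowns.** Airways from one scan may vary together, and correlation shrinks the shift in the airway-averaged median, as tabulated. The share of subjects with both measures rising (10 airways, s = 0.2 and 0.3) falls from 32% and 44% under independence to 12% and 18% at correlation 0.3. Protocol 1.3 sets CT exposure to reach the noise index needed for analysis, and the study plan (Protocol Table 1) allows the end-of-treatment scan only after a good-quality baseline scan. Both favour smaller s. At s = 0.1 the shift in the mean is only 2%.
- **The treatment comparison mostly survives.** With a true 10% widening, equal s, six airways and correlation 0.3, the differences between arms are +10.1, +10.2 and +10.5 points for LA and -17.7, -18.7 and -20.9 for R at s = 0.1, 0.2 and 0.3. Both were positive in at most 0.8% of simulated trials. A general claim that the treatment comparison is reversed is not supported; reversal needs unequal variability.
- **The pooling phrase.** Read literally, averaging over all segmental parameters could be taken to mix lumen area, wall area and wall area %. That is strained: the resistance bullet uses the same phrase with only one quantity, and SAP 4.2.6.1 plots the three measures separately.
- **Ratios are already promised.** Section 6 does promise them, and SAP 4.1 would summarise them by geometric mean. But 3.2.3.2 and 4.1 say otherwise, so the output actually produced is undetermined.

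**Conclusion.** The point holds as a limited defect in an exploratory, descriptive summary. The within-arm mean percent change in resistance is shifted upward by exp(2s²) - 1 when lumen area does not change: +2.0%, +8.3% and +19.7% at assumed s = 0.1, 0.2 and 0.3. The airway-averaged median is shifted too, by about 5% and 12% at s = 0.2 and 0.3 with 10 airways and correlation 0.3. These sizes rest on normal log changes and on values of s and correlation that the documents do not give.

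Lumen area and resistance rising together is impossible for one airway, but it is quite possible for arithmetic means over airways or subjects. A reader might infer that such a result is certain in both arms; it is a risk that grows with s. Nor does the large-airway objective rest on CT alone, since SAP 1.1.4 and 3.2.3.2 list biopsy outcomes under it as well. The primary analysis and the sample size are untouched. Separately, 3.2.3.2 and 4.1 contradict Section 6 on whether ratios are produced, and that needs settling whatever s turns out to be.

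**What to change.** In SAP 3.2.3.2, compute log(Week 12/baseline) for each airway. Average the logs over airways, separately for lumen area, wall area, wall area % and resistance, and say explicitly that the average is over airway locations within one measure. Report the geometric mean ratio by arm, with percent change given as 100 x (ratio - 1). Apply the same scale to RB1 and LB1+2. Replace "For these analyses, only the percent change will be considered" accordingly, and amend the exploratory-variable rule in SAP 4.1 so that both sections agree with Section 6.

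The cost is SAP wording and minor programming. The CT data are the same and no new measurement is needed.

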#### 3.2.3.3 Effect on small airway obstruction

The change from baseline to Week 12 (Visit 9) will be calculated as described in Section 3.1.2 for the following exploratory endpoints:

- R5-R20 and AX as evaluated by AO
- Sacin by using MBW

- Air trapping expressed as percentage of the lung with expiratory density less than -856 HU, and as expiratory-to-inspiratory ratio of mean lung density on CT
- Regional matching of the inspiratory/expiratory CT scans to assess air trapping/small airway obstruction
- Extent of gas trapping determined from physiologic testing by TLC/RV, VC/IC, FRC

For the Sacin parameter, the value used for the analyses will be the average of the records of day of all quality values (1 or 2) – quality=3 records will not be considered for the analyses. Once the daily value is obtained, the usual baseline/ visit window defined in this SAP will apply.

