#### 5.1.6 Airwave oscillometry

Airwave oscillometry (AO) is a non-invasive lung function test included in this study to evaluate treatment effect on small airway physiology.

A calibrated system will be used for measurements. Detailed procedures for performing, recording and analysing AO data will be described in a separate manual.

AO evaluation will be performed in accordance with the schedule provided in Table 1. Assessment at Visit 2 will be a training manoeuvre for the subjects.

By measuring subject's airflow and response to sound waves, frequency-dependent resistance and reactance will be calculated by the AO system software. A signed and dated copy of the results printout from the equipment must be kept at the study site for SDV. The printout must be marked with the study code, subject enrolment code, date and time of measurement, and visit number. Number of parameters including (but not limited to) R5, R20 and AX for each trial will be recorded and analysed.

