#### 3.1.2 Absolute and percent change from baseline

Absolute change from baseline outcome variables is computed as

(post-randomization value – baseline value).

Percent change from baseline is computed as

((post-randomization value – baseline value) / baseline value)  $\times$  100%.

Ratio of post-randomization value to baseline value is computed as

(post-randomization value / baseline value).

For the analysis of ratios, a log transformation is required. If either the post-randomization value or the baseline value is missing, then the absolute or percent change from baseline or the ratio value will also be set to missing.

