The primary and secondary variables will be analysed using geometric means. Both the difference in number and the % change or ratio will be reported, but the statistical analysis will only be based on the ratio. All hypothesis testing will be reported using 2-sided tests. P-values will be rounded to 4 decimal places. No adjustment for multiplicity will be performed and nominal p-values will be reported.

For the efficacy analyses except PRO/ SNOT-20 data, if the value of the ratio of Week 12 to baseline is zero and both Week 12 and baseline are not missing, the ratio will be replaced, for the analysis of ratio only (including for descriptive statistics), by half the smallest observed ratio among the randomized subjects with non-zero values (both treatment arms). For the corresponding non descriptive analyses on the ratio, values of baseline equal to zero were replaced by half the smallest observed value among the subjects with non-zero for the calculation of the baseline logtransformed covariate,

For the efficacy analyses except PRO/ SNOT-20 data, if the baseline value is zero, the baseline will be replaced, for the analysis of ratio to baseline or percent change from baseline only (including for descriptive statistics), by half the smallest observed value among the randomized subjects with non-zero values and among all records (baseline and post baseline

for both treatment arms). If both the baseline and post-baseline record are zero, then the percent change is zero.

QQ plots of residuals of the primary and secondary efficacy analysis models (both on absolute change and log-transformed ratio) will be created.

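### Percent change from baseline is planned for R5-R20, a difference that can be zero or negative; with a negative baseline its sign reverses, and the SAP has no rule for this

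*SAP*

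**What the plan says.** Protocol 5.1.6 treats the two resistances as separate measurements: "Number of parameters including (but not limited to) R5, R20 and AX for each trial will be recorded and analysed". R5-R20 is therefore read here as the difference between them.

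SAP 3.2.3.3 introduces the small-airway list with "The change from baseline to Week 12 (Visit 9) will be calculated as described in Section 3.1.2 for the following exploratory endpoints", and its first entry is "R5-R20 and AX as evaluated by AO". Section 3.1.2 defines three measures of change: absolute, percent and ratio. The percent formula has the core "post-randomization value – baseline value) / baseline value", so the denominator carries its sign. For the third measure it adds: "For the analysis of ratios, a log transformation is required".

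SAP 4.1 says which measures are reported. For this class of variable, "exploratory efficacy variables will summarise absolute and percent change"; ratios are assigned to the primary and secondary variables. SAP Section 6 says otherwise: "ratios will also be calculated for sputum, serum, large and small airways remodelling variables". A further item there extends all three types of change to every exploratory endpoint.

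SAP 4.1 also handles zeros. A zero baseline is replaced, for ratio and percent change, "by half the smallest observed value among the randomized subjects with non-zero values and among all records", pooling baseline and later records from both arms. A zero ratio is replaced in the same manner by half the smallest non-zero ratio. If baseline and later value are both zero, the percent change is set to zero. Only PRO/SNOT-20 data are exempt. Negative values are not mentioned.

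**The concern.** Percent change and ratio to baseline have a clear meaning only when values are positive. A difference of two resistances has no floor at zero, and no eligibility criterion in Protocol 3.1 or 3.2 sets one.

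Three things follow if the plan is applied as written. A negative baseline turns a fall into a positive percentage and a rise into a negative one. A baseline close to zero turns a trivial absolute change into a percentage large enough to drive the arm mean. And the zero rule, which presumes positive data, can replace a zero by a negative number, because the smallest non-zero record is then a negative one.

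At stake is the readability of one exploratory table. The mean percent change could contradict the mean absolute change beside it, with no prior statement of which to believe or of what to do with values that cannot be computed.

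**Working it through.** The documents state no figure for R5-R20, so there is none to reproduce. The check applies the SAP formulas to worked values and then asks how often the problem would occur.

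**1. Worked values** (illustrative). Percent change = 100 × (post − baseline) / baseline; ratio = post / baseline.

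| Baseline | Week 12 | Absolute | Percent | Ratio | Log ratio |
|---|---|---|---|---|---|
| 0.20 | 0.10 | −0.10 | −50% | 0.5 | −0.693 |
| 0.10 | −0.02 | −0.12 | −120% | −0.2 | undefined |
| −0.02 | −0.05 | −0.03 | +150% | 2.5 | +0.916 |
| −0.02 | 0.06 | +0.08 | −400% | −3 | undefined |
| 0.01 | 0.06 | +0.05 | +500% | 6 | +1.792 |

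Rows 1 and 2 have positive baselines, and the percent change keeps the right sign even when the value crosses zero. Row 3 shows a fall as a rise, and its log ratio is defined but points the wrong way. Row 4 shows a rise as a fall. Row 5 has the right sign but an extreme size. Absolute change is right in every row.

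**2. Zero rule.** If the smallest non-zero record is −0.05, a zero baseline becomes −0.05 / 2 = −0.025. A rise to 0.05 is then 100 × (0.05 + 0.025) / (−0.025) = −300%, or 100 × 0.05 / (−0.025) = −200% if the numerator keeps the original zero. Either way a rise is reported as a fall.

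**3. Frequency, under assumed values.** Model: a true subject value, normal with mean μ and SD s; independent visit error with SD e; records rounded to 0.01; a true fall of 0.03 in every subject; 35 subjects per arm; the SAP zero rule taken literally. Units are taken as kPa·s/L.

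- Set A, (μ, s, e) = (0.15, 0.12, 0.04), (0.12, 0.12, 0.05), (0.10, 0.10, 0.05).
- Set B, (0.20, 0.10, 0.04) and (0.25, 0.10, 0.04), where non-positive baselines are rare.

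Because of rounding, the share of baselines at or below zero is Φ(−(μ − 0.005) / √(s² + e²)). For (0.10, 0.10, 0.05) this is Φ(−0.095 / 0.1118) = 20%. For (0.25, 0.10, 0.04) it is Φ(−0.245 / 0.1077) = 1%.

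| Simulated quantity | Set A | Set B |
|---|---|---|
| Baselines at or below 0 | 13-20% | 1-4% |
| Subjects whose percent change has the wrong sign | 11-18% | 1-3% |
| Subjects with a negative ratio | 8-15% | 1.5-4% |
| Arms whose mean percent change is an increase | 16-21% | 9-12% |
| Arms whose median percent change is an increase | under 1% | under 1% |
| Arms whose mean absolute change is an increase | under 1% | under 1% |

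The last row can be checked directly. The standard error of the mean absolute change is e√(2/35), which is 0.0096 for e = 0.04 and 0.0120 for e = 0.05. Then 0.03 / 0.0096 = 3.1 and 0.03 / 0.0120 = 2.5, so the wrong-sign probability is about 0.1% to 0.6%.

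**4. Sensitivity.** Sets A and B imply a within-subject correlation s² / (s² + e²) of 0.80 to 0.90. A bivariate normal model with a mean fall of 0.3 SD gives more undefined logs: with 20% negative baselines, 17.7% of subjects at correlation 0.8 and 26.6% at 0.5. With no negative baselines, the same model shows no sign reversals and no undefined logs.

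**The case against.** The strongest reply is that little depends on this. R5-R20 is exploratory, summarised descriptively and not tested. Being listed first gives it no priority among the small-airway measures, and absolute change is already planned. SAP 4.1 also reports the median with the mean, and the median percent change keeps the right direction in over 99% of simulated arms. All of this stands, and it limits the severity.

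It can also be said that the frequency rests on assumptions. That is correct: the documents give no R5-R20 distribution, and the population is uncontrolled, reversible asthma, in which negative values may be uncommon. But Set B shows that the mean percent change stays unreliable when only 1-4% of baselines are at or below zero, because small denominators are enough.

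A reader might go further and infer that improvements in R5-R20 are generally scored as worsening, that its log ratios are undefined, and that subjects who cross zero are silently dropped. The documents do not support this. Reversal needs a negative baseline, or a zero baseline replaced by a negative number; falls from a positive baseline are shown correctly, and the error also runs from worsening to improvement. The log fails only when the two values differ in sign. Whether a ratio is computed at all is unsettled between SAP 4.1 and Section 6. Nothing says how undefined logs would be programmed, and SAP 4.1 requires N with each ratio summary. Zero ratios should not be counted as undefined either, since SAP 4.1 replaces them, although that rule too could select a negative value.

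**Conclusion.** The percent-change rule for R5-R20 is wrong as written. It is a stated formula that gives the wrong sign for any negative baseline, backed by a zero rule that can create one. Two readings are needed: that R5-R20 is R5 minus R20, which Protocol 5.1.6 supports, and that such a difference can be non-positive, which is arithmetic.

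The size is conditional. If about 1-20% of baselines are at or below zero, percent change has the wrong sign in about 1-18% of subjects, and the mean percent change shows an increase in about 9-21% of arms despite a true fall of 0.03. A ratio, if computed, would be negative in about 1.5-15% of subjects under the same model. The median percent change and the mean absolute change are wrong in under 1% of arms. No primary, secondary or safety conclusion is affected. Severity: minor.

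**What to change.** - In SAP 3.2.3.3, state that R5-R20 is summarised by absolute change only, with no percent change, ratio or zero replacement. The SAP already restricts measures by variable: 3.2.3.2 limits the CT airway morphology and resistance measures to percent change.
- In SAP 4.1, restrict the zero-replacement rule to variables that cannot be negative, and base it on half the smallest positive value observed. The rule already carries an exemption for PRO/SNOT-20, so this extends an existing device.
- Reconcile SAP 4.1 with Section 6 on whether ratios are computed for the other small-airway variables.

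The cost is SAP wording and the loss of the percent-change summary, and any ratio summary, for one exploratory variable. No data collection or sample size changes. Within R5-R20, every sign reversal and undefined value disappears.
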